### **Interventions (Sessions 2 – 4).**

○ **Transcranial alternating current stimulation (tACS).** TACS will be applied at 6 Hz for the Verum tACS group and 1 Hz tACS for the Frequency Control group because higher frequencies of stimulation (above theta) may introduce visual flickering (or phosphenes) that could confound the interpretation of the data (Paulus, 2010; Schutter & Hortensius, 2010). Moreover, 1-Hz tACS has not been associated with cognitive alterations (Antal et al., 2008; Castillo Saavedra et al., 2014) and we have verified its use as a control in Preliminary Study 1. A sinusoidal alternating current of 1mA peak amplitude (2mA peak-to-peak amplitude) will be delivered via a pair of Ag/AgCl electrodes ( $3.14\text{ cm}^2$ ) through a Starstim-32 device (Neuroelectrics, Spain) while patients are engaged in a tablet-based cognitive task (EVO, see below). During each session, participants will receive 20 min of stimulation with a 15-s ramp up and 15-s ramp down. The stimulation electrodes will be located at F3 and F4 of the 10–20 electrode coordinate system (above PFC). Impedance will be kept below 10 kΩ. In order to confirm that the frequency control was an appropriately blinded manipulation and all patients tolerate tACS well, all patients will be asked to complete a 1-min survey to scale the perception of stimulation (headache, scalp pain, tingling, burning sensation) from 1 (mild) to 10 (severe) at the end of each session. If the score on the stimulation perception survey is below 4 for each item, tACS will be considered well-tolerated.

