**c. Potential Risks:**

- **Electroencephalography:** There are no known risks associated with EEG procedures, all of which have been used extensively in previous research. Conventional EEG recording and sensory stimulation techniques with standard subject grounding procedures are always employed. Some electrode paste may remain on the scalp, but it can be easily removed with shampooing.
- **Transcranial alternating current stimulation:** Although uncommon, tACS has some risk for headache, dizziness, nausea, itchy sensation, irritation under the area of the electrodes and the sensation of shock. TACS has also been reported to cause brief flashes of light ("phosphenes") in humans, but these are not discomforting. Should an adverse effect occur in a participant, that participant will be excluded from continuing the intervention. The protocol described here uses stimulation levels that fall well within safety limits established by basic research investigating neural tissue damage and other possible physiological effects in both humans and animals. Overall, tACS is generally considered a safe, noninvasive and painless technique for modulating neural excitability.

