**Adequacy Of Protection Against Risks.**

**a. Recruitment and Informed Consent:** Participants will be recruited from the UCSF Center for MS and Neuroinflammation, a clinic that sees over 6,000 patients annually with MS and related disorders. All participants will participate in the informed consent process. They will be familiarized with the protocol by the experimenter, including risks and benefits, and informed consent will be documented according to the regulations governing human beings as experimental participants at the University of California, San Francisco.

**b. Protection Against Risks:** All participants will be under close supervision throughout the experiments. All tACS, and EEG recordings are done with state of the art technology. Equipment is routinely screened to assure all components, cables etc are in perfect working condition and standard grounding techniques are always employed. All information collected from the proposed experiments will remain strictly confidential, except as required by law, and will be made available to the participant and his/her physician upon the participant's request. Personal identification of a subject will be excluded from all scientific communications. TACS studies are closely monitored for subject comfort and tACS will be discontinued if stimulation ever feels painful. Low intensity tACS (2mA peak-to-peak

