or less) will be used in the proposed studies, and research utilizing similar stimulation parameters as proposed here have reported no adverse mental or health effects lasting longer than the testing session in normal healthy subjects. Much care will be taken to ensure that stimulation parameters are within the range of published safety guidelines. Although no cases of seizures have been reported using tACS with the proposed stimulation parameters, participants will be screened for past occurrence of seizure and a family history of epilepsy as part of the inclusion/exclusion process. Participants will be fully informed of all procedures and the known and potential risks associated with tACS. Trained personnel will be present during all experimental procedures and all research staff are required to maintain current CPR certification. Drs. [name] (PI), [name] (co-PI), [name] (co-investigator) and [name] (co-investigator) will distinguish between a serious adverse event from a non-serious adverse event and an unanticipated problem. In response to an adverse event, [name], a board-certified neurologist at the UCSF Multiple Sclerosis Center, will monitor participants until they are either deemed fit to go home or are directed to the UCSF Medical Center for additional care. In over 33,000 sessions with over 1,000 participants using stimulation similar to the proposed protocol, there is no evidence for irreversible injury produced by transcranial electrical stimulation (tES) protocols within a wide range of stimulation parameters ( $\leq 40$  min,  $\leq 4$  mA). This includes a wide variety of participants, including persons from potentially vulnerable populations. The analysis consolidates and adds to existing evidence on tES safety and facilitates further research of tES in human subjects (Bikson et al., 2016). A more recent review article suggested that safety is established for low-intensity conventional tES defined as  $<4$  mA, up to 60 min duration per day. Using tACS stimulation, fewer adverse effects were reported compared to tDCS. In specific paradigms with amplitudes of up to 10 mA, frequencies in the kHz range appear to be safe (Antal et al., 2017).

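### The rule that declares tACS well tolerated has no item for dizziness or nausea and ignores participants whose stimulation was stopped for an adverse effect or pain

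*Combined protocol and SAP*

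**What the plan says.** Under the heading for interventions in sessions 2 to 4, participants are asked to "scale the perception of stimulation (headache, scalp pain, tingling, burning sensation) from 1 (mild) to 10 (severe) at the end of each session". The survey has two stated purposes, namely to confirm that "the frequency control was an appropriately blinded manipulation and all patients tolerate tACS well". The decision rule follows: "If the score on the stimulation perception survey is below 4 for each item, tACS will be considered well-tolerated". No further item and no free-text line is listed.

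In the human-subjects part, under potential risks, the protocol states that "tACS has some risk for headache, dizziness, nausea, itchy sensation, irritation under the area of the electrodes and the sensation of shock". Phosphenes are mentioned separately: "TACS has also been reported to cause brief flashes of light", with the remark that they cause no discomfort.

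Three other provisions deal with adverse effects. Under potential risks: "Should an adverse effect occur in a participant, that participant will be excluded from continuing the intervention". Under adequacy of protection against risks: "tACS will be discontinued if stimulation ever feels painful". The same section says that the investigators "will distinguish between a serious adverse event from a non-serious adverse event and an unanticipated problem", and that a neurologist follows anyone with an adverse event until that person can go home or is sent for further care. None of these provisions refers to the tolerability rule, and the rule does not refer to them.

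**The concern.** The survey is meant to support a positive statement, that all patients tolerate the stimulation, and it comes with a pass mark. A pass mark can only reflect what is asked. If the protocol itself expects certain effects and the survey does not ask about them, a clean result says nothing about those effects, yet the rule would still be read as covering tolerability in general.

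A second gap makes the first one worse. Stopping stimulation for an adverse effect is plain evidence that a participant did not tolerate it, but the rule is defined on survey scores alone. The two sections can therefore give opposite answers for the same person.

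At stake is one conclusion of the trial: whether a report that tACS was well tolerated in people with MS would be supported by the data collected.

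**Working it through.** The plan states no figure to reproduce here. The check sets the two lists side by side and then applies the rule to cases that the plan allows.

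**Step 1. Compare the lists.** The six effects come from the potential-risks section and the four items from the interventions section.

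| Effect named as a risk | Survey item of the same name | Closest item, read generously |
|---|---|---|
| Headache | Headache | Headache |
| Dizziness | None | None |
| Nausea | None | None |
| Itch | None | Tingling |
| Irritation under the electrodes | None | Scalp pain or burning |
| Sensation of shock | None | Tingling |

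- Matched by name: 1 of 6.
- Matched generously: 1 + 3 = 4 of 6.
- Unrated on every reading: 6 − 4 = 2 of 6 (dizziness and nausea).

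Phosphenes are also unrated. They are left out of the count because the protocol lists them apart and describes them as not discomforting.

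**Step 2. Apply the rule to an unasked symptom.** Take a participant with severe nausea who scores 1 on all four items. Every score is below 4, so the rule is met.

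**Step 3. Add the stopping provisions.**

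- The participant in step 2 has an adverse effect and is taken off the intervention under the potential-risks section. The four scores do not change, so the rule is still met.
- A second participant finds the stimulation painful, rates scalp pain 3, and has stimulation stopped under the adequacy-of-protection section. Since 3 is below 4, the rule is met again. This case involves an item that the survey does include, so longer item lists alone do not remove the conflict.

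Both cases assume that the survey is completed in the session where stimulation stops. The plan does not say whether it is, or how sessions that a withdrawn participant never attends are counted.

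**Step 4. Look at the scale.** It runs from 1 (mild) to 10 (severe), with no score for an absent symptom. Adding nausea and dizziness on the same scale would record at least mild nausea and dizziness in everyone.

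**Step 5. Look for another source that closes the gap.** The pain and fatigue questionnaires (BPI and MFIS) are given to all participants, but at sessions 1 and 5, and stimulation is given only in sessions 2 to 4. The adverse-event text describes the response once an event is known. It sets no scheduled question about dizziness or nausea and does not feed the rule.

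**The case against.** Several points on the other side are sound.

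- **The count depends on how names are matched.** A reader might infer that five of the six risks are invisible to the survey, and that even severe skin irritation would pass. The documents do not support that. Severe irritation under a scalp electrode would probably raise the scalp-pain or burning score, and tingling may pick up itch or shock. The firm gap is dizziness and nausea.
- **Symptoms are not left unmanaged.** A reader might infer that a dizzy participant could leave the lab unattended. The protocol provides close supervision, trained staff at every procedure, withdrawal after an adverse effect, and neurologist follow-up before the participant goes home.
- **The survey is not the only collection of symptoms.** BPI and MFIS are collected too. The survey is the only one the plan ties to the stimulation sessions.
- **The background does not call tACS untried in MS.** It says, to the authors' knowledge, that effects on cognition in MS have not been assessed. It makes no statement about earlier exposure or tolerability.
- **The unit is not stated.** The rule speaks of tACS being well tolerated and does not say whether it is judged per participant, per session or on group scores. This stands as a further ambiguity, but it does not rescue the rule: a symptom that is never asked about cannot enter the judgement at any of these levels.
- **Tolerability is not a listed outcome.** It is not among the primary, secondary or exploratory measures, and no power statement depends on it. That limits the importance of the point. It does not remove it, because the plan gives the rule a purpose and a threshold, and so a conclusion will be drawn from it.

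**Conclusion.** The point holds for the tolerability conclusion. The rule leaves at least two of the six named bodily effects unrated on any reading, and five of six by name. It can also be met by participants whose stimulation was stopped for an adverse effect or for pain. Followed as written, it can return a favourable answer that the protocol's own safety provisions contradict, so the sections must be reconciled. This is more than missing detail, but it is confined: adverse-event management, the efficacy analyses and the power statements are untouched.

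The conclusion assumes that the four items in the text are the whole survey and that the rule is applied to survey scores alone, as written.

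A reader might also try to size the problem from the small sample. With no flagged participant, the exact two-sided 95% upper limit is 1 − 0.025^(1/n): 1 − 0.025^(1/40) = 8.8% for both arms together and 1 − 0.025^(1/20) = 16.8% for one arm. These limits would be the same for any survey with no flagged participant, whatever it asked. They are a reason to report counts with intervals, and do not measure this defect.

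**What to change.** 1. In the interventions section, add to the end-of-session survey: dizziness, nausea, itching, skin irritation under the electrodes, sensation of shock, and one open line for anything else. Give every item a score for an absent symptom.
2. Reconcile the tolerability rule with the potential-risks and adequacy-of-protection sections, so that the tolerability statement also accounts for participants whose stimulation was stopped for an adverse effect or for pain. Keep these participants in the denominator. This changes the reporting only and leaves the stopping provisions as they are.
3. State the unit as the participant, over all stimulation sessions. For each arm, report the number with any item at 4 or above (the plan's own threshold) or stopped early, with an exact 95% confidence interval.

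**Cost.** The survey grows from 4 to 4 + 5 + 1 = 10 lines. The plan describes it as taking one minute. If time scales with the number of lines (an assumption), the extra is 6/4 × 60 = 90 seconds per session, or 3 × 90 = 270 seconds over the three stimulation sessions. There is one more table, and the tolerability statement may look slightly less favourable.

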## Recruitment and Retention Plan

**Recruitment.** Participants will be recruited from the UCSF Center for MS and Neuroinflammation, a clinic that sees over 6,000 patients annually with MS and related disorders, with a track record of mHealth studies and trials including those led [name]. Patients will be recruited via multiple channels:

- Study investigators or staff will identify prospective subjects through chart review. For prospective participants who have been deemed eligible, coordinator will contact their clinician for permission to contact in-person at their scheduled visit, or by phone at a later date.
- Direct referral from affiliated clinicians -- study staff will follow up in person, on the phone, or over email.
- The study will be listed on ClinicalTrials.gov with contact information for responsible research staffs.

In our experience, these are generally sufficient, but if additional participants are required, Advertisements (flyers, brochures, radio or TV ads, posting on clinical research sites or social media, presentation of the study at community events/media, etc.) will be distributed. In the rare occurrence that these recruitment methods do not yield sufficient participation, we will contact previous patients from our other studies who have expressed interest in future research with us.

**Retention.** The proposed research requires participants to come into our lab at UCSF for 5 visits over 2 weeks. Our retention plan will focus on patient comfort and engagement. Physical comfort is achieved by placing participants in an adjustable ergonomic chair that is designed for long periods of seated activity. Additionally, breaks are offered as needed to get up, walk around, and use the restroom. Finally, water and light snacks are offered to our participants. Psychological comfort is first achieved by training all research personnel in how to be courteous and friendly with participants over email, phone and in person. Next, our research space is painted in warm and inviting colors and decorated to facilitate a relaxing experience. Finally, psychological comfort is achieved by clearly explaining the consent forms, their rights, and the tasks that the participant will be engaged in so there is no confusion or unease – and offering participants multiple opportunities to ask questions. Regarding engagement, participants are given information about the experiment that highlights the importance of this work in broader context without compromising the integrity of the experimental design. Next, the research paradigms are created to be optimally challenging, such that they are never too hard so as to be frustrating, nor are they too each so as to be boring. We believe that optimally challenging cognitive functions is the ideal way not just to keep participants engaged in the research, but will more likely yield better data. Together, our efforts to provide a comfortable and engaging research experience has historically served us well to retain participants.

## Preliminary Studies

- **Preliminary study 1.** We have previously demonstrated (and replicated) that theta-tACS above PFC is able to enhance divided attention abilities in healthy young adults with a large effect size ( $d = 0.96$ ) ([name] et al., 2019; [name] et al., 2017). More recently, we replicated these effects again in healthy older adults (aged 60 – 80 years) and further demonstrated that this improvement in attention sustains for at least a month following the last tACS treatment (manuscript in preparation). Moreover, the improvements in divided attention were correlated with increases in PFC theta activity. Although we did not assess processing speed, we did observe changes in response times during the divided attention task, suggesting processing speed may have contributed to (or co-occurred with) the improvements in divided attention. *These studies support the notion that the proposed tACS approach is a promising for treatment for cognitive decline in MS – specifically divided attention and processing speed (Specific Aim 1).* In this preliminary study, we also observed tACS effects were positively correlated with the magnitude of the individual MRI-based modeled electric field in the brain. *This provides support for our hypothesis that anatomical factors affect tACS outcomes (Specific Aim 2).*

- **Preliminary study 2.** We have recently demonstrated the utility of the proposed experimental paradigm (i.e. EVO) and the proposed processing speed outcome measure in people with MS. Specifically, in a behavioral intervention study, MS patients who played EVO improved information processing speed ( $p=0.003$ ) ([name] et al., 2019). In a follow-up randomized controlled pilot trial, the mean increase in SDMT was 6.10 for EVO task group compared with 3.55 for an active control group, with clinically improvement significantly more likely to be retained for at least two months in the EVO group ([name] et al., 2019). *These preliminary results provide additional support for the feasibility of using the proposed experimental paradigm in MS and the selection of outcome measures for Specific Aim 1.* In this preliminary study, we also demonstrated that SDMT improvement was found to be associated with clinical severity, which revealed that clinical data contributes to the change of SDMT scores. This shows that, *given the heterogeneity of MS, understanding individual variability is critical for clinical trials assessing cognitive function interventions in MS, and underscores the importance of Specific Aim 2* ([name] et al., 2019).

## Statistical Design and Power

**Power.** Twenty participants in a group will correspond with  $>80\%$  power ( $1-\beta$ ) at a 95% significance level ( $1-\alpha$ ) as calculated from our preliminary studies (detailed below).

**Primary outcome measure: Divided attention.** Results from Preliminary Study 1 showed that Verum (6 Hz) tACS, and not control tACS, yielded improved divided attention discrimination performance in healthy adults, as indexed by d-prime ( $F(1,35) = 6.63$ ,  $p = 0.01$ ,  $\eta_p^2 = 0.16$ ). Here, it is hypothesized that MS patients who receive Verum tACS will exhibit comparable performance gains in divided attention. To test this, a divided attention index will be calculated from performance during the discrimination task as the cost in d-prime (i.e., d-prime dual task minus d-prime single task). Data will be submitted to an ANCOVA with Group (Verum, Control) and Session (pre-tACS, post-tACS) as factors. Although age will be matched across groups, age will serve as the covariate to account for within-group differences. A Group x Session interaction is expected to show that the Verum tACS group, compared to the control group, will exhibit a larger reduction in d-prime cost post-tACS, indicating enhanced divided attention ability. For this interaction, 20 participants per group will yield  $>95\%$  power ( $1-\beta$ ) at a 95% significance level ( $1-\alpha$ ) with an expected effect size of  $f = 0.28$ .

**Primary outcome measure: Processing speed.** Results from Preliminary Study 2 showed that cognitive training with EVO improves processing speed, as indexed by the SDMT score ( $t(17) = 3.19$ ,  $p = 0.005$ ,  $d = 0.34$ ). Here, it is hypothesized that MS patients who receive Verum tACS will exhibit comparable performance gains in processing speed. To test this, SDMT score will be submitted to an ANCOVA with Group (Verum, Control) and Session (pre-tACS, post-tACS) as factors. Although age will be matched across groups, age will serve as the covariate to account for within-group differences. A Group x Session interaction is expected to show that the Verum tACS group, compared to the control group, will exhibit a higher SDMT score post-tACS, indicating enhanced processing speed. For this interaction, 20 participants per group will yield 80% power ( $1-\beta$ ) at a 95% significance level ( $1-\alpha$ ) with an expected effect size of  $f = 0.19$ .

**Secondary outcome measure: Frontal theta power.** Results from Preliminary Study 1 also showed that the Verum tACS group, and not control tACS, exhibited a correlation between divided attention and frontal theta power such that those participants with the greatest increase in frontal theta power yielded the greatest improvement in divided attention ability ( $r = 0.50$ ,  $p = 0.04$ ). Here, it is hypothesized that MS patients who receive Verum tACS will exhibit similar neuroplastic changes in frontal theta activity. To test this, frontal theta power will be extracted during the discrimination task (theta dual task minus theta single task) and a change score will be calculated (post-tACS minus pre-tACS). A regression analysis will be conducted between theta power and the change in the divided attention index (post-tACS minus pre-tACS) described above. It is expected that increases in theta power only the Verum tACS group will be related to improvements in divided attention ability. To further characterize between group differences, theta power will be submitted to an ANCOVA with Group (Verum, Control) and Session (pre-tACS, post-tACS) as factors. Although age will be matched across groups, age will serve as the covariate to account for within-group differences. A Group x Session interaction is expected to show that the Verum tACS group, compared to the control group, will exhibit a larger increase in theta power post-tACS, indicating enhanced neuroplasticity. For this interaction, 20 participants per group will yield  $>95\%$  power ( $1-\beta$ ) at a 95% significance level ( $1-\alpha$ ) with an expected effect size of  $f = 0.28$ .

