## Study Design

**Overall strategy.** We will enroll forty adult MS patients (aged 18-65 years) randomly assigned to one of two groups: either a Verum (6 Hz) tACS group or a Frequency Control (1 Hz) group. Twenty participants in each group will correspond with >80% power ( $1-\beta$ ) at a 95% significance level ( $1-\alpha$ ) as calculated from our preliminary studies. The two groups will be age-matched. A randomized double-blinded, placebo controlled, multi-session

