#### Outcome measures (Sessions 1 and 5).

- **Primary outcome measure: Divided attention (Specific Aim 1).** This (and all) outcome measure(s) will be assessed at baseline (pre-tACS; session 1) and at follow-up (post-tACS; session 5). Divided attention will be measured by a divided attention task module (Table 1). The divided attention module is comprised of 3 tasks: visual perceptual discrimination (single task), visuomotor tracking (single

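### Adjusting the Group x Session tests for the session 1 score would be a cheap efficiency gain: about 6-8% narrower intervals at a pre-post correlation of 0.65, none at about 0.9

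*Combined protocol and SAP*

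**What the plan says.** In the Combined protocol and SAP, Statistical Design and Power, three group comparisons share one model:

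- Divided attention (primary): "Data will be submitted to an ANCOVA with Group (Verum, Control) and Session (pre-tACS, post-tACS) as factors".
- Processing speed (primary): "SDMT score will be submitted to an ANCOVA with Group (Verum, Control) and Session (pre-tACS, post-tACS) as factors".
- Frontal theta power (secondary): "theta power will be submitted to an ANCOVA with Group (Verum, Control) and Session (pre-tACS, post-tACS) as factors".

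In each case the Group x Session interaction is tested, and one covariate is named: "Although age will be matched across groups, age will serve as the covariate to account for within-group differences". The plan does not say whether age enters as a main effect or is crossed with Session.

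Study Design says that patients are "randomly assigned to one of two groups". Outcome measures (Sessions 1 and 5) says: "This (and all) outcome measure(s) will be assessed at baseline (pre-tACS; session 1) and at follow-up (post-tACS; session 5". A baseline value therefore exists for every outcome.

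For SDMT the power statement is: "For this interaction, 20 participants per group will yield 80% power", at f = 0.19. For divided attention and theta it is more than 95% at f = 0.28. No pre-post correlation is given for any of them.

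**The concern.** The word ANCOVA suggests adjustment for baseline, but the covariate is age and the session 1 score is only a level of Session. With two sessions, the interaction estimate is the difference between groups in mean change. A change score fixes the slope of post on pre at 1. A model with the session 1 score as a covariate estimates that slope, and it has smaller error variance whenever the true slope is not 1.

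Age may not help either. As a main effect only, it leaves the interaction estimate and its standard error unchanged; it acts on the interaction only if crossed with Session.

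What is at stake is precision. With 20 per group, and SDMT planned at 80%, efficiency available from data already collected is worth having if it is material. The question is whether it is.

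**Working it through.** **Inputs.** N = 40 (20 per group), f = 0.19 for SDMT and f = 0.28 for divided attention and theta, alpha 0.05, and the SDMT pilot t(17) = 3.19 with d = 0.34, all from Statistical Design and Power. Assumed because the plan does not say: a two-sided test, no dropout, age unrelated to the scores, and a range for rho and for k = post SD / pre SD.

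**1. Reproduce the plan's power.** Standard repeated-measures interaction formula: lambda = f^2 x 40 x 2/(1 - rho), on 1 and 38 df.

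- f = 0.19, rho 0.65: lambda = 0.0361 x 80/0.35 = 8.25, power 79.9%. Exactly 80% needs rho = 0.651.
- A one-sided test would need rho of about 0.55.
- f = 0.28, rho 0.65: lambda = 0.0784 x 80/0.35 = 17.92, power 98.5%. More than 95% only requires rho of at least 0.542.

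**2. What the cited SDMT result implies.** The standardised mean change is 3.19/sqrt(18) = 0.752, so d = 0.34 is not on that scale. If d used the raw SD, rho = 1 - (0.34/0.752)^2/2 = 0.898. The plan's SDMT figures thus point to about 0.65 by one route and about 0.90 by another.

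**3. Error variance, pre SD set to 1.**

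- Change score: 1 + k^2 - 2 rho k.
- Adjusted: k^2(1 - rho^2).
- Difference: (1 - rho k)^2, which vanishes when the baseline slope rho k equals 1.
- With k = 1, the ratio adjusted/change is (1 - rho^2)/[2(1 - rho)] = (1 + rho)/2.

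**4. CI width, adjusted relative to change, k = 1, 20 per group.** The large-sample value is sqrt((1 + rho)/2). The simulated values include the cost of estimating the covariates (40,000 trials per cell; first figure with age balanced between groups, second unbalanced).

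| rho | Large sample | Simulated |
|---|---|---|
| 0.5 | 0.866 | 0.879, 0.891 |
| 0.65 | 0.908 | 0.922, 0.934 |
| 0.8 | 0.949 | 0.963, 0.976 |
| 0.9 | 0.975 | 0.990, 1.003 |
| 0.95 | 0.987 | 1.003, 1.017 |

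Break-even is at rho of about 0.89 to 0.94, depending on how age enters the change-score model.

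**5. Unequal SDs.** These figures take age as uninformative and, in effect, absent from the change-score test.

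- At rho 0.65 the ratio is 0.88 at k = 0.9, 0.97-0.98 at k = 1.1 and 1.00 at k = 1.2.
- Over k from 0.9 to 1.2 and rho from 0.5 to 0.95, the best case is 0.84 (k = 0.9, rho 0.5).
- The worst case is 1.03 (k = 1.1, rho 0.9, where the slope is 0.99).

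**6. Power, k = 1.** Adjusted lambda = change lambda x 2/(1 + rho), on 1 and 36 df.

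- SDMT, f = 0.19, rho 0.65: 8.25 x 2/1.65 = 10.00, so power goes from 79.9% to 86.8% (simulated 84.8% to 85.6%).
- SDMT, f = 0.19, rho 0.9: 99.9% with either model.
- If the effect is resized so that change-score power is 80% at rho 0.9, adjusted power is 80.5% (age balanced) or 79.6% (unbalanced).
- Divided attention, f = 0.28, rho 0.65: 98.5% to 99.5%.

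**7. Validity.** Simulated type I error at rho 0.5, 0.65 and 0.9 was 0.049 to 0.051 for the change-score test and 0.048 to 0.051 for the adjusted test.

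**The case against.** The strongest reply is that nothing here is broken. The plan names a model, its factors, a covariate and the tested term, and under randomisation that test is valid and unbiased. A reader might infer bias or an inflated error rate; neither the documents nor the simulation supports that.

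A second reply is that SDMT, where margin looks tightest, may gain nothing. The only observed SDMT data in the plan suggest rho of about 0.90. That stands, with two limits: it assumes d was scaled by the raw SD, and it rests on 18 patients. The competing 0.65 is not data; it is back-solved from a power sentence and assumes a two-sided test and one formula. A reader might also infer that SDMT is underpowered. The documents do not show this, because power at f = 0.19 depends on the unstated rho and would be 99.9% at 0.9.

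A third reply is that the equal-SD gains are not general. This also stands. The plan expects response to stimulation to vary between individuals, so a post-session SD above the pre-session SD is plausible, and at k = 1.2 the gain at rho 0.65 disappears.

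Finally, a larger gain for divided attention could be argued from the effect implied by the preliminary F(1,35) = 6.63. That needs that study's group sizes, which the documents do not give, and it replaces the planned f = 0.28, where the gain is about 1 point.

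None of this counts against adjusting. The gain is uncertain, but the possible loss is small.

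**Conclusion.** The point holds as a cheap improvement, not as a correction of an error. The three planned Group x Session tests are change-score comparisons that leave out the session 1 score as a covariate.

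The benefit is conditional. It is useful if rho is about 0.65 or lower with similar SDs at the two sessions, and nil if the baseline slope is near 1. Over the range examined (SD ratio 0.9 to 1.2, rho 0.5 to 0.95) the adjusted interval is between about 16% narrower and about 3% wider. That asymmetry, and not any single figure, is the reason to adjust.

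All sizes assume 20 completers per group and age unrelated to the scores; the power figures also assume equal SDs and a two-sided test. The point does not extend to the regression of theta change on divided-attention change, which uses change scores by design.

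**What to change.** - For divided attention, SDMT and the theta group comparison, prespecify: post-tACS score = Group + pre-tACS score + age. Use a two-sided test of Group, and report the adjusted mean difference with its 95% CI.
- Keep Group x Session as a sensitivity analysis, and state whether age enters as a main effect or as Age x Session.
- Restate the three power figures for the chosen model, with an explicit rho and its source.
- Leave the theta regression as planned.
- Settle this before unblinding.

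The cost is one error degree of freedom for the baseline score, some rewriting of Statistical Design and Power, and an interval up to about 3% wider if the baseline slope turns out near 1. No new data, visits or patients are needed.
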